8.3. Discontinuation Criteria

A patient is considered discontinued from study treatment when the decision to permanently stop TAS-114 or S-1 for the TAS-114/S-1 arm and S-1 for the S-1 control arm is made, including those decisions made during TAS-114 or S-1 interruptions and recovery periods.

Study drug should be continued whenever possible. In the event study drug is stopped, it should be determined if the stop can be made temporarily; permanent study drug discontinuation should be a last resort. If the decision to discontinue TAS-114 or S-1 is made within 2 weeks after the

patient's last treatment visit, an End of Treatment visit is not required unless deemed clinically necessary by the investigator. If the decision to discontinue TAS-114 or S-1 (because of disease progression or other reasons) is made more than 2 weeks after the last treatment visit, the End of Treatment visit is required.

Any TAS-114 or S-1 discontinuation should be fully documented.

8.3.1. End of Treatment Discontinuation Criteria

The reason for discontinuation should be documented in the source documents.

Patients can be withdrawn from treatment for the following reasons:

- At their own request at any time irrespective of the reason.
- RECIST-defined disease progression of solid tumors.
- Clinical progression.
- Unacceptable adverse events (AEs), or change in underlying condition such that the patient can no longer tolerate therapy, as evidenced by:
 - A maximum dose delay >14 days from the scheduled start date of the next cycle.
 - Need for more than 2 dose reductions of study drug (maximum of 2 dose reductions allowed as described in [Section 9.1.2.1.](#))
- Investigator's decision including need for other anticancer therapy not specified in the protocol, or surgery or radiotherapy to the only site(s) of disease being evaluated in this protocol.
- Pregnancy.

If there is strong evidence of clinical benefit and reasons to justify continuation of TAS-114 or S-1 dosing even though treatment discontinuation criteria have been met, this decision must be reviewed with the sponsor on a case-by-case basis, and continuation of therapy may be allowed assuming all other treatment resumption criteria have been met.

Upon discontinuation of treatment the investigator is to ensure the following:

- The clinical research associate must be notified immediately; and
- The Study Treatment Discontinuation form in the electronic case report form (eCRF) must be completed, specifying the primary reason for the patient's withdrawal from treatment.

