9.1.2.2. TAS-114 and S-1 Dose Reductions for Treatment-related Toxicities

TAS-114 dose reductions are to be applied in case of a toxicity according to the criteria described below. The TAS-114 dose will be reduced by a dose level, for a maximum of 2 dose levels (see [Section 9.1.2.1](#)). Should the toxicities that require further dose reduction recur after the second dose reduction, the affected patient should be discontinued from treatment.

If dose modification fails to result in achieving minimal criteria to resume treatment, the investigator should remove the patient from study treatment.

S-1 dose reductions are to be applied concurrently for all TAS-114 dose reductions (see [Section 9.1.2.1](#)).

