13.1.5. Pregnancy

If a patient becomes pregnant while in the study, the study treatment must be immediately discontinued. Pregnancy information in a female patient should be reported **within 24 hours** from the time the investigator first becomes aware of a pregnancy or its outcome. This should be performed by completing a Pregnancy Form and faxing it to Taiho Pharmacovigilance or designee.

New and/or corrected information regarding the pregnancy obtained after submitting the Pregnancy Form must be submitted by faxing an updated Pregnancy Form to Taiho Pharmacovigilance or designee.

If the outcome of the pregnancy is a stillbirth, congenital anomaly/birth defect, or a serious event in the mother, report as an SAE to Taiho Pharmacovigilance or designee.

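### The conditional continuation clause in Protocol 8.3.1 excludes no criterion, so it conflicts with the firm stops for pregnancy (13.1.5) and for a delay over 14 days (9.1.2.3)

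*Protocol*

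**What the plan says.** Protocol 8.3.1 introduces its list with "Patients can be withdrawn from treatment for the following reasons". The list includes the patient's own request, RECIST progression, clinical progression, unacceptable adverse events (shown by a delay of more than 14 days or a need for more than 2 dose reductions), the investigator's decision, and pregnancy.

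The paragraph after the list creates an exception. Where there is strong evidence of benefit and a justification, it provides for "continuation of TAS-114 or S-1 dosing even though treatment discontinuation criteria have been met". It adds that "this decision must be reviewed with the sponsor on a case-by-case basis" and that "continuation of therapy may be allowed assuming all other treatment resumption criteria have been met". No listed reason is excluded.

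Three other sections of the protocol deal with the same situations:

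- 13.1.5: "If a patient becomes pregnant while in the study, the study treatment must be immediately discontinued".
- 9.1.2.3: a patient whose next cycle would be delayed by more than 14 days is to be taken off the study. The verb is *will*.
- 9.1.2.2: "Should the toxicities that require further dose reduction recur after the second dose reduction, the affected patient should be discontinued from treatment". The same section adds: "If dose modification fails to result in achieving minimal criteria to resume treatment, the investigator should remove the patient from study treatment".

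SAP 7.3 makes it a deviation reportable in the clinical study report when a patient meets withdrawal criteria but stays on treatment.

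**The concern.** An investigator who works from 8.3.1 sees reasons for which a patient can be withdrawn, followed by a route to continue dosing that is open to all of them. The parent section, 8.3, also leans towards continuing, since it treats permanent discontinuation as a last resort. An investigator who works from 13.1.5 or 9.1.2.3 sees a firm stop with no route to continue. No section refers to the other or says which prevails.

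The first thing at stake is safety. For pregnancy and for prolonged delay, the protocol should give one instruction, and it gives two. The second is reporting. A patient kept on treatment with the sponsor's agreement complies with 8.3.1 but departs from 13.1.5 or 9.1.2.3. Whether that patient is counted under SAP 7.3 then depends on which section is taken to define the withdrawal criteria.

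**Working it through.** No arithmetic applies. The numerical limits agree across sections: at most 2 dose reductions in 8.3.1, 9.1.2.1 and 9.1.2.2, and at most a 14-day delay in 8.3.1 and 9.1.2.3. What differs is how binding the stop is.

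| Situation | In 8.3.1 | Elsewhere | Result |
|---|---|---|---|
| Pregnancy | *can*, open to the exception | 13.1.5: *must*, immediately | Direct conflict |
| Delay over 14 days | *can*, open to the exception | 9.1.2.3: *will* | Direct conflict |
| Toxicity needing a further reduction after the second | *can*, open to the exception | 9.1.2.2: *should* | Weaker tension |
| Minimal resumption criteria not reached | exception requires resumption criteria to be met | 9.1.2.2: *should* remove | Consistent |

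The next question is whether the three conditions of the exception would keep these patients out of it.

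1. *Strong evidence of clinical benefit.* This concerns how the patient is doing on treatment. A patient who is pregnant or late in starting a cycle may satisfy it.
2. *Case-by-case sponsor review.* This is a safeguard, but it is a step before a decision. Section 13.1.5 asks for an immediate stop and provides for no such step.
3. *All other resumption criteria met.* The criteria in 9.1.2.2 to 9.1.2.4, including Tables 9 to 11, concern toxicity grade, neutrophils, platelets and creatinine clearance. None mentions pregnancy. For a delay, the word *other* suggests that the criterion being waived is set aside, so a patient who recovers after day 14 could satisfy the rest.

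The conditions narrow the exception but do not remove pregnancy or prolonged delay from it.

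For repeat toxicity the reading is different. Section 9.1.2.2 uses *should*, and the 8.3.1 paragraph is written for cases in which criteria for stopping have been met, so the two can be read as a rule and its exception. What is missing is a cross-reference.

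**The case against.** Four arguments stand against the point.

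*The verb alone contradicts nothing.* The list reads as the set of recognised withdrawal reasons. It begins with the patient's own request, which cannot be optional. Stopping a pregnant patient satisfies both *can* and *must*. This stands. The conflict comes from the continuation paragraph, which excludes no reason, and not from the verb by itself.

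*The specific rule governs the general one.* Section 13.1.5 is specific and unconditional, and the pregnancy test, contraception and exclusion requirements point the same way. That is a sensible reading, but the protocol states no order of precedence, and the exception is worded to apply after criteria have been met.

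*The toxicity rules allow discretion elsewhere.* Section 9.1.2 lets the investigator continue at the same dose for events judged unlikely to become serious or life-threatening, and 9.1.2.2.1 requires discussion with the Medical Monitor where continuing after Grade 3 or higher non-hematologic events is uncertain. This stands, and it is one reason why the 9.1.2.2 limb is only a tension.

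*The consequence for the analysis is small.* SAP 7.3 lists and tabulates deviations, and refers to a Protocol Deviation Plan that is not among the documents and may settle how an agreed continuation is classed. SAP 7.5.1 analyses PFS in the ITT population, so a deviation removes nobody. This also stands.

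A reader might infer that the protocol lets dosing continue freely after any stopping criterion, or instructs dosing in pregnancy. The documents do not support that: three conditions apply, continuation is only a possibility, and 8.3.1 nowhere says that a pregnant patient may continue.

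**Conclusion.** The inconsistency is real. It is direct for pregnancy (8.3.1 against 13.1.5) and for a delay over 14 days (8.3.1 against 9.1.2.3), and weaker for toxicity that recurs after the second reduction (8.3.1 against 9.1.2.2).

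Its frequency cannot be stated, because the documents give no rate for any of the three situations. A reader might take the toxicity limb to cover everyone who reaches the second reduction. It covers only those whose toxicity then recurs and calls for a further reduction. The case for acting rests on what could follow for an affected patient and on how little the correction costs, not on the expected number of patients.

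The effect is on patient safety and deviation reporting. Sample size and the ITT analysis of PFS are unaffected. The conclusion assumes that no text outside these documents, such as the Protocol Deviation Plan, already sets the order of precedence.

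**What to change.** The sponsor should reconcile Protocol 8.3.1, 9.1.2.2, 9.1.2.3 and 13.1.5. For each reason listed in 8.3.1, the protocol should state whether stopping is mandatory or optional and whether the continuation paragraph can apply. The other three sections should carry the same instruction or refer to that list. SAP 7.3 should use the list to define its category for patients who met withdrawal criteria but were not withdrawn, and should say how a continuation agreed with the sponsor is classed.

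No view is taken here on which clinical rule is right; each situation needs a single instruction.

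The cost is a clarification letter or a protocol amendment and a matching line in the SAP. Sample size, endpoints and planned tests do not change.

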8.4. Patient Numbering and Treatment Allocation

All patients will sign an informed consent form (ICF) and be assigned a unique patient number. The patient numbering process is defined in the Case Report Form Completion Manual.

Investigative sites must complete all relevant eCRFs for all enrolled patients, even if the patient is not treated with study drug.

Randomization will take place once the consented patient has completed all the necessary baseline procedures and is deemed eligible for study entry. Treatment assignment will be done centrally using a dynamic allocation method (biased coin) via an IXRS stratified by:

- Geographical region (Region 1: Asian [Japan]; Region 2: Western [Europe and US])
- Histological subtype (nonsquamous cell carcinoma [including mix] and squamous cell carcinoma).

8.5. Replacement Criteria

No patients will be replaced at any time during this study.

8.6. Prohibited Medications and Therapies

Patients are not permitted to receive any other investigational or any other anticancer therapy, including chemotherapy, immunotherapy, biological response modifiers, or antineoplastic endocrine therapy during the study treatment period.

Palliative radiotherapy is not permitted while the patient is receiving study treatment.

Other fluoropyrimidine-group antineoplastic agents such as 5-FU, tegafur, or flucytosine are not permitted within 7 days after withdrawal of TAS-114/S-1 or S-1.

The following drugs are prohibited:

Medication	Reason for Exclusion
Sorivudine	Enhances S-1/5-FU activity
Brivudine	Enhances S-1/5-FU activity
Uracil	Enhances S-1/5-FU activity
Eniluracil	Enhances S-1/5-FU activity
Folate/Folinic acid	Enhances S-1/5-FU activity
Cimetidine	May enhance S-1/5-FU activity
Dipyridamole	May enhance S-1/5-FU activity
Nitroimidazoles including metronidazole & misonidazole	May enhance S-1/5FU activity
Methotrexate	May enhance S-1/5FU activity
Clozapine	May increase risk and severity of hematologic toxicity with S-1
Allopurinol	May diminish S-1/5-FU activity
Phenytoin	S-1 may enhance phenytoin activity
Flucytosine (a fluorinated pyrimidine antifungal agent)	May enhance S-1/5-FU activity
Coumarin-derivative anticoagulant including warfarin	S-1 may enhance activity of coumarin-derivative anticoagulant

8.7. Concomitant Medications and Therapies

8.7.1. Concomitant Medications and Therapies

The following medications/therapies may be given concomitantly under the following guidelines:

Hematologic Support

Administer hematologic support as medically indicated (eg, blood transfusions, granulocyte colony-stimulating factor [G-CSF]) according to the institutional site standards. If there are no standard procedures for the use of growth factors, follow the American Society of Clinical Oncology (ASCO) Guidelines for Use of Hematopoietic Colony-Stimulating Factors available at www.asco.org.

Management of Diarrhea

Educate both patients and patients' families and/or caregivers regarding the potential seriousness of chemotherapy-induced diarrhea. Instruct patients to immediately contact the clinical site staff at the first sign of a loose stool.

If there are no institutional standards, refer to the guidelines published by Benson AB et al in *Journal of Clinical Oncology*.²²

In addition, patients should be instructed to report to the investigator or his or her designee the relevant information concerning their use of antidiarrheal medication and any episodes of diarrhea they experience.

Management of Nausea/Vomiting

Administer antiemetics as clinically indicated. If there are no institutional standards refer to the ASCO Guidelines for Antiemetics in Oncology.²³

Drug interactions with TAS-114

Drug interaction studies have not been conducted. The following information is based on results from in vitro studies and clinical phase 1 study. Caution is advised if these drugs are given concomitantly (see Appendix E, Classification of Substrates, Inhibitors, and Inducers of Cytochrome P450 Isoenzymes and Transporters).

CYP3A4/5 inhibitors

CYP3A4/5 inhibitors may increase the concentration and activity of TAS-114. Care should be exercised when TAS-114 is co-administered with CYP3A4/5 inhibitors.

CYP3A4 inducers

CYP3A4 inducers may decrease the concentration and activity of TAS-114. Care should be exercised when TAS-114 is co-administered with CYP3A4 inducers.

CYP3A4/5 substrates

TAS-114 may decrease the concentration and activity of CYP3A4/5 substrates. Care should be exercised when TAS-114 is co-administered with CYP3A4/5 substrates.

Drug interactions with S-1

Other fluoropyrimidines

Co-administration of other fluoropyrimidines such as capecitabine, 5-FU, tegafur, or flucytosine can lead to additive toxicities, and is contraindicated. A minimum washout period of 7 days is recommended between administration of S-1 and other fluoropyrimidines.

Sorivudine and brivudine

Sorivudine or its chemically-related analogues such as brivudine irreversibly inhibit DPD, resulting in a significant increase in 5-FU exposure. This may lead to increased clinically significant fluoropyrimidine-related toxicities with potentially fatal outcomes. S-1 must not be used with sorivudine or brivudine or within 4 weeks of the last dose of sorivudine or brivudine.

CYP2A6 inhibitors

As CYP2A6 is the major enzyme responsible for the conversion of tegafur to 5-FU, co-administration of a known CYP2A6 inhibitor and S-1 should be avoided as effectiveness of S-1 could be decreased.

Folate/folinic acid

Metabolites of folinate/folinic acid will form a ternary structure with thymidylate synthase (TS) and FdUMP, potentially increasing the cytotoxicity of 5-FU. Caution is advised as folinic acid is known to enhance the activity of 5-FU.

Nitroimidazoles, including metronidazole and misonidazole

No data are available on the concomitant use of nitromidazoles with S-1. However, nitromidazoles may reduce clearance of 5-FU and thus increase plasma levels of 5-FU. Caution is advised as co-administration may increase the toxicity of S-1.

Methotrexate

No data are available on the concomitant use of methotrexate with S-1. However, polyglutamated methotrexate inhibits thymidylate synthase and dihydrofolate reductase, potentially increasing cytotoxicity of 5-FU. Caution is advised as co-administration may increase the toxicity of S-1.

Clozapine

No data are available on the concomitant use of clozapine with S-1. However, due to possible additive pharmacodynamic effects (myelotoxicity), caution is advised as co-administration may increase the risk and severity of haematologic toxicity of S-1.

Cimetidine

No data are available on the concomitant use of cimetidine with S-1. However, co-administration may decrease clearance and, thus increase plasma levels of 5-FU. Caution is advised as co-administration may increase the toxicity of S-1.

Coumarin-derivative anticoagulant

The activity of a coumarin-derivative anticoagulant was enhanced by S-1. Caution is advised as co-administration of S-1 and coumarin anticoagulation therapy may increase the risk of bleeding.

Phenytoin

Fluoropyrimidines may increase phenytoin plasma concentration when administered concomitantly with phenytoin causing phenytoin toxicity. Frequent monitoring of phenytoin blood/plasma levels is advised when S-1 and phenytoin are administered concomitantly. If indicated, the dose of phenytoin should be adjusted according to the phenytoin Summary of Product Characteristics (SmPC). If phenytoin toxicity develops, appropriate measures should be taken.

Other

Based on non-clinical data, allopurinol may decrease antitumor activity due to suppression of phosphorylation of 5-FU. Therefore, concurrent administration with S-1 should be avoided.

8.7.2. Effective Contraception During Study

Female patients who are considered not to be of childbearing potential must have a history of being postmenopausal (no menses for 12 months without an alternative medical cause), or hysterectomy that is clearly documented in the patient's source documents (see [Section 8.2.1](#)).

For WOCBP, including female study participants and partners of male participants, effective contraception is defined as follows:

- combined (estrogen and progestogen containing) hormonal contraception associated with inhibition of ovulation:
 - oral
 - intravaginal
 - transdermal
- progestogen-only hormonal contraception associated with inhibition of ovulation:
 - oral
 - injectable
 - implantable
- intrauterine device
- intrauterine hormone-releasing system
- bilateral tubal occlusion
- vasectomized partner with documentation of the success of the vasectomy
- complete abstinence from heterosexual intercourse (periodic abstinence is not a safe method)

Male patients with partners who are WOCBP should use a combination of male condom with either cap, diaphragm or sponge with spermicide during the trial and for 6 months after the last dose of study drug.

8.8. Dietary Restrictions

TAS-114 and S-1 should be taken orally BID with a glass of water at least 1 hour before or after a meal.

9. STUDY DRUG

Compliance to all study drug regimens should be documented in the patient’s source documents.

9.1. Study Drug Administration and Dose Modification Procedures

9.1.1. Treatment Regimen

Each TAS-114/S-1 and S-1 treatment cycle will be 21 days: 14 days of treatment and 7 days of recovery. TAS-114 and S-1 will be administered orally BID with a glass of water at least 1 hour before or after a meal.

Study sites will call/login to the IXRS at the beginning of each patient treatment cycle to record the current cycle number, record the patient’s current weight and obtain the patient’s BSA, and obtain the recommended study medication dosage of S-1.

The BSA will be calculated by the IXRS using the following DuBois formula (all BSA calculations are rounded to 2 decimal places).

$$BSA (m^2) = ([Body Weight (kg)]^{0.425} \times [Height (cm)]^{0.725}) \times 0.007184$$

If at the beginning of the next treatment cycle, a patient’s body weight decreases by $\geq 10\%$ from baseline, the IXRS will recalculate the patient’s BSA and provide the site with the adjusted study medication dosage.

9.1.1.1. TAS-114/S-1 Arm Drug administration

Days 1 through 14: TAS-114 and S-1 orally BID (with a glass of water at least 1 hour before or 1 hour after completion of morning and evening meals) with the first dose administered in the morning of Day 1 of each cycle and the last dose administered in the evening of Day 14.

Days 15 through 21: Recovery. See required number of study drugs for TAS-114 ([Table 6](#)) and S-1 ([Table 7](#)).

Table 6: Number of TAS-114 Tablets per Dose

Tablets per dose (2x daily every 12 h)	
TAS-114 Dose (2x daily)	100 mg tablets/dose (pale-yellow)
400 mg	4
300 mg	3
200 mg	2

Extension of TAS-114/S-1 treatment into the recovery period is not permitted.

Any missed doses reported by the patient should be recorded in the patient’s source documents.

Table 7: Number of S-1 Capsules per Dose

S-1 Dose (2x daily)	BSA (m ²)	Dosage in mg (2x daily)	Total daily dose (mg)	Capsules per dose (2x daily every 12 h)	
				15 mg (brown/white)	20 mg (white)
30 mg/m ² /dose	≥2.25m ²	70	140	2	2
	2.09-2.24m ²	65	130	3	1
	1.92-2.08m ²	60	120	0	3
	1.75-1.91m ²	55	110	1	2
	1.59-1.74m ²	50	100	2	1
	1.42-1.58m ²	45	90	3	0
	1.25-1.41m ²	40	80	0	2
	≤1.24m ²	35	70	1	1
25 mg/m ² /dose	≥2.25m ²	60	120	0	3
	2.09-2.24m ²	55	110	1	2
	1.92-2.08m ²	50	100	2	1
	1.75-1.91m ²	45	90	3	0
	1.59-1.74m ²	40	80	0	2
	1.42-1.58m ²	40	80	0	2
	1.25-1.41m ²	35	70	1	1
	≤1.24m ²	30	60	2	0
20 mg/m ² /dose	≥2.25m ²	50	100	2	1
	2.09-2.24m ²	45	90	3	0
	1.92-2.08m ²	40	80	0	2
	1.75-1.91m ²	35	70	1	1
	1.59-1.74m ²	35	70	1	1
	1.42-1.58m ²	30	60	2	0
	1.25-1.41m ²	30	60	2	0
	≤1.24m ²	20	40	0	1

9.1.1.2. S-1 Arm Drug Administration

S-1 should only be given on Days 1 through 14 of each cycle even if doses are missed or held for any reason during Days 1 through 14. See required number of study drugs in [Table 7](#) (S-1).

Extension of S-1 treatment into the recovery period is not permitted.

Any missed doses reported by the patient should be recorded in the patient’s source documents.

